## 4 STUDY DESIGN

### 4.1 OVERALL DESIGN

The study will use a randomized cross-over design. It will be structured by division into two phases. Both phases will examine the acute cardiovascular response to cannabis consumption,

both at rest and during exercise. *Phase I* will examine if and how this response differs whether cannabis is smoked or vaporized. *Phase II* will examine how this response is influenced by cannabinoid concentration within inhaled cannabis. Phase II of the current study will use a single-blind design, with participants being unaware of the relative cannabinoid concentrations of the cannabis they consume. Cannabis will be inhaled using methods of smoking (phase I only) or vaporization (phase I and II). Each experimental study visit (study visits 2-9), 100mg of cannabis will be consumed via one of the two aforementioned methods of inhalation, followed by a subsequent rest period, or by 20 minutes of exercise. Primary endpoints will be examined pre- and post-consumption each visit (with the exception of muscle sympathetic nerve activity, which will only be performed on a single study visit), while secondary endpoints will be recorded during exercise.

Each phase of the study will require participants to complete an introductory and control visit, as well as 4 experimental study visits, where cannabis inhaled under alternating conditions (phase I: smoking vs. vaporizing high THC cannabis, phase II: high CBD cannabis vs. high THC cannabis) followed by exercise, or a time-matched rest period. The order in which these visits will occur will be randomized, and individualized for each participant. A within-subjects design will be utilized, so that each participant completes each condition. High THC cannabis used will be the cannabis strain “Rex”, while the high CBD strain will be “Kalea”. The dose size and strength will not be altered throughout the course of the study.

Continuous blood pressure, heart rate, and electrocardiogram monitoring will occur prior to, and during cannabis administration (prior to exercise) on all visits where cannabis is consumed. This procedure will be followed throughout the entirety of the 40-minute cannabis consumption period. If either systolic or diastolic blood pressure exceeds 160mmHg or 90mmHg at rest, respectively, exercise will not be performed, and the study visit will not continue. If heart rate exceeds 100bpm or falls below 40bpm at rest, exercise will not be performed, and the study visit will not continue.

All research will be performed within the department of Human Health and Nutritional Sciences at the University of Guelph.

There are no planned interim analyses planned for the current trial.

A sub-group analysis will be performed, with participants divided by sex, to determine the existence of any sex differences in primary and secondary endpoints.

## 4.2 SCIENTIFIC RATIONALE FOR STUDY DESIGN

A within subject design has been chosen for this study due to potential variability in primary endpoints between individuals. Specifically, variation in pulse wave velocity and flow-mediated dilation. Published reference values for pulse wave velocity in our selected age group may range between 3.92m/s and 8.26m/s. This substantial range requires a within-subjects design to allow for meaningful assessment of the effects of cannabis on arterial stiffness. Similar to pulse wave velocity, flow-mediated dilation may vary substantially between and within subjects, with values as high as 20% reported in healthy individuals. This design is further warranted due to the choice of secondary endpoints. Exercise performance, and the accompanying physiological responses, are highly dependent on numerous factors that are likely to vary between individuals. Such factors include weight, fitness level, and familiarity with cycling. This further warrants the need for a within subject design, as these variables would have to be

matched if using parallel groups. Even if groups were matched, there is a strong likelihood that significant variability would exist in performance metrics.

The proposed study does not employ a placebo-control or a double-blind design. This is a consequence of the challenge owed to masking the device used to inhale cannabis in phase I. Vaporization and smoking are distinct methods of cannabis inhalation, and as such different devices must be used, making blinding difficult. A single-blind design will be utilized in phase II, in that participants will not be aware of the strain of cannabis they are consuming. Although collection will not be double-blind, investigators will be blind to condition during data analysis.

Randomization of the order of experimental visits in each phase will occur to combat improvement in performance as a result of better of pacing strategies, or improvements in fitness. Randomization will be performed using a randomization software ([www.random.org](http://www.random.org)). The order in which visits will occur will be individualized to each participant.

### 4.3 JUSTIFICATION FOR DOSE

For all cannabis administration a standard 100mg dose of dried cannabis flower will be consumed by smoking or vaporization. Depending on the experimental condition, cannabis will be either Rex (13.6±2.7% THC, <0.5% CBD dry weight) or Kalea (<1% THC, 14.5±2.9% CBD dry weight). This dose will not be altered throughout the course of the study and will be given to all participants.

A 100mg dose of dried cannabis flower was selected based upon published recommendations suggesting that maximum daily cannabis use for individuals prescribed medical cannabis should not exceed 400mg daily, and should be consumed over 4 doses each day. The selection of this singular dose was also made with consideration to the context of the cannabis use in the selected population. The current study will examine recreational cannabis users, who have consumed cannabis in the past year whose use has not exceeded an average of twice per week. Given that recreational users are being examined, the quantity of commercially available products for recreational use was used to inform the dosage. In Ontario, cannabis is sold nearly exclusively through the Ontario government's online platform (<https://ocs.ca>). This online platform features a large range of pre-rolled cannabis products that contain 0.33-1g of dried cannabis flower with THC and CBD concentrations up to 28% dry weight and 13% dry weight, respectively. Although this 100mg dose of Rex and Kalea may be seemingly small, previous evidence indicates that a dose of this size is sufficient to elicit cardiovascular responses to smoking and vaporization of cannabis.

A recent summary of the safety of CBD indicate that a dosage of 15-160mg of CBD have been used in studies with no ill effects. Additionally, the dose of ~15mg of CBD was chosen to closely parallel the CBD content of inhaled products commercially available through the Ontario government. There is currently no evidence examining the effect of CBD on primary endpoints of the present study. It is therefore difficult to quantify how CBD impacts primary outcomes. Thus, selecting dose based on safety and ecological validity was used as the primary justification.

### 4.4 END OF STUDY DEFINITION

A participant is considered to have completed the study if he or she has completed either phase I or phase II of the study including the last scheduled procedure shown in the Schedule of Activities (SoA), Section 1.3.

## 5 STUDY POPULATION

### 5.1 INCLUSION CRITERIA:

To be eligible to participate in each phase study, an individual must meet all of the following criteria:

1. Provision of signed and dated informed consent form
2. Stated willingness to comply with all study procedures and availability for the duration of the study
3. Male or female, aged 19-45yr
4. In good general health as evidenced by medical history and free of chronic disease
5. Must be experienced with cannabis use. This requires recreational cannabis use of a minimum of once per week in the past 30 days as confirmed by urine test
6. Experience consuming cannabis recreationally by vaping dried cannabis

### 5.2 EXCLUSION CRITERIA

An individual who meets any of the following criteria will be excluded from participation in this study:

1. **Deemed unfit to exercise by the PARQ+.**  
The goal of the present study is to examine the acute cardiovascular response to cannabis consumption at rest and during exercise. As such participants must be able to safely complete the pre-determined exercise protocol.
2. **Current or past diagnoses of substance abuse disorder**
3. **Failure of recreational substance urine screening test**
  - **Substances to be tested for include: Cocaine, Crack, Morphine, Heroin, Fentanyl, Amphetamines, Ecstasy, Methamphetamine, Spice and AB-Pinaca (synthetic cannabis), Methcathinones, LSD, and Ketamine.**
4. **Current, past, or strong family history of psychosis, or has previously experienced a cannabis-related psychotic episode**
5. **Current or past diagnoses of cannabis use disorder**
6. **Current or past diagnoses of any mood or anxiety disorder**  
Exclusion criteria 2-5 will be implemented to ensure that no individuals are enrolled in the study who could carry an elevated risk of experiencing a severe cannabis related adverse event (such as cannabis induced hyperemesis, or a psychotic episode). Each of these exclusion criteria represent contraindications for cannabis prescription.
7. **Identified ECG abnormalities**
8. **Systolic blood pressure exceeding 160mmHg**
9. **Diastolic blood pressure exceeding 90mmHg**
10. **Resting heart rate exceeding 100bpm, or lower than 40bpm**
11. **Diagnosed with respiratory disease**
12. **Diagnosed with cardiovascular disease**
13. **Diagnosed with liver disease**

**14. Diagnosed with kidney disease**

Individuals with cardiovascular, respiratory, liver, or kidney diseases will be excluded from this study as primary and secondary endpoints may be confounded by disease states.

**15. Is Pregnant or planning to be pregnant**

It is not currently established how cannabis consumption by a pregnant woman impacts a developing fetus. As such, females who are planning to be, or are pregnant will be excluded as a precautionary measure.

- a. Female subjects of childbearing potential and male subjects when sexually active with a female of childbearing potential must agree to use contraception for the duration of the trial.
  - i. For female subjects of childbearing potential, contraception methods include:
    1. A highly effective method of contraception (such as oral hormonal contraceptives, IUD, IUS, bilateral tubal ligation);
    2. Double barrier method defined as the use of a male condom with cervical cap/diaphragm with spermicide;
    3. Male partner with a confirmed successful vasectomy; OR
    4. Abstinence defined as refraining from heterosexual intercourse consistent with the preferred and usual lifestyle of the subject.
  - ii. For male subjects when sexually active with a female of childbearing potential, contraception methods include
    1. Vasectomy (confirmed successful);
    2. Condom with spermicide; OR
    3. Abstinence defined as refraining from heterosexual intercourse consistent with the preferred and usual lifestyle of the subject.

**16. Currently taking prescription medication (excluding contraceptive medication)****17. Is a cigarette smoker**

It is well established that cigarette smoking negatively impacts numerous endpoints evaluated in the current study. As such no cigarette smokers will be included.

**5.3 LIFESTYLE CONSIDERATIONS**

The day of each experimental visit, participants are asked to:

- Refrain from cannabis consumption for the 48 hours prior to the beginning of each visit. (Confirmed by urine THC test, positive test result will result in rescheduling)
- Refrain from consumption of alcohol for the 24 hours prior to the beginning of each visit.
- Refrain from exercising vigorously for 24 hours prior to the beginning of each visit.
- Refrain from caffeine consumption for 8 hours prior to the beginning of each visit.
- Refrain from vitamin supplementation for 8 hours prior to the beginning of each visit.
- Fast for 6 hours prior to the beginning of each visit
- Avoid operating a motor vehicle for the entirety of the date of a study visit where cannabis is consumed
- Arrange to have a trusted individual escort them to their residence following completion of their study visit.

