## 2.3 RISK/BENEFIT ASSESSMENT

### 2.3.1 KNOWN POTENTIAL RISKS

Largely owing to elicit status, a comprehensive risk profile of cannabis consumption has not been developed. There does, however, exist a number of immediate and long-range risks. It has been established that consumption of cannabis containing THC results in impairments in cognition and memory. In addition to these impairments, users may experience panic attacks. The most severe psychological risk of consuming cannabis is the development of a mild to severe psychotic episode, which occurs on rare occasions. The diverse effects of cannabis on the brain have resulted in the recommendation that cannabis should not be consumed prior to operating motor vehicles. Impairment may typically last between 3-4 hours, with some evidence indicating that in impairment can persist for 6-8 hours.

In addition to immediate psychological risks, cannabis consumption is associated with a number of physical risks. Smoking cannabis can result in a transient sinus tachycardia. Reports have associated cannabis use with acute cardiovascular events and stroke, although a causative relationship has not been established. Despite these physical risks, cannabis is largely considered safe. In rare instances, cannabis consumption can induce hyperemesis.

Cannabis use may also present immediate economic risks to some individuals. Due to the long-standing elicit status and the only recent legalization of recreational use, many employers still prohibit cannabis use by employees.

Long-range risks of cannabis use are less understood than acute risks. Physical and psychological risks have been identified, however, certain long-range risks have not been directly attributed to cannabis itself, due to the existence of certain behaviors or requisite activities associated with use. Physical long-range risks include reductions in pulmonary function, respiratory infection, and alterations in brain structure. Long-term cannabis use has been associated with an increased rate of development of schizophrenia, mood and

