Despite lacking a robust list of potential benefits of recreational use in healthy individuals, the justification for an investigation into the acute physiological effects of consumption is counter balanced by the rarity of acute adverse effects entirely attributable to cannabis use in these individuals. Cannabis induced hyperemesis and cannabis induced psychotic episodes are rare. While other more consequential risks of cannabis use such as acute coronary syndrome and stroke have been suggested, no investigation has identified a causal relationship. These reported acute cardiovascular risks are especially intriguing given the increasing popularity of use by athletes in and out of competition. Exercise is a potent transient cardiovascular stress, and many questions surrounding the effects of the combined stimulus of exercise and cannabis remain. Despite reports of acute risks of cannabis consumption, it should be noted that presently a much larger evidence-base suggests that recreational cannabis use is associated with long rather than short term health consequences.

Although the acute risks of cannabis use appear to be rare, current knowledge suggests that they may be inherent to use and therefore should be minimized, but cannot be completely avoided. An effective approach to ensuring participant safety in the context of cannabis use requires pre-eminent planning in the case of known acute risks, and selection of a population that does not possess an elevated risk of experiencing the most commonly reported adverse effects. The present study will monitor participants following cannabis consumption to ensure participant safety. Participants will be monitored until the effects of cannabis have subsided. Further, a dosage has been selected that is less potent and smaller than what is available for typical recreational use. Choice of dosage was selected as a dose that is likely to exert physiologically meaningful effects, but not impose elevated risk to participants. Participants in the present study will be experienced users, who will not be unfamiliar with the effects of consumption. Additionally, participants possessing commonly known risk factors that may predispose to acute risk will be excluded.

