## 6.2 PREPARATION/HANDLING/STORAGE/ACCOUNTABILITY

### 6.2.1 ACQUISITION AND ACCOUNTABILITY

Aurora Cannabis Inc. will provide the exact amounts of Rex and Kalea needed for the completion of the study by 20 individuals. As the required sample size has been determined to be 20 individuals, with each participant consuming 100mg of cannabis on four separate occasions, per phase of study, 12 grams of Rex and 4 grams of Kalea will be required. An additional 3 grams of Rex and an extra gram of Kalea will be purchased to account for the potential of participant drop-out. Cannabis will be stored in a locked safe in a room with restricted access. Only members of the investigatory team will have access to the room where the cannabis is stored, and the room will not be accessed alone by any researcher. The safe will be secured to the wall of the room. Each entry to the room for the access of cannabis will be recorded in a log, where time of exit and entry, and purpose of entry will be recorded. Additionally, all cannabis will be immediately inventoried upon receipt, and a constant record will be kept of how much cannabis is removed at any time. Cannabis will be organized into pre-weighed 100mg samples, and will be labelled by sample number. Any time cannabis is removed, the responsible individual will be required to record what sample was removed. Weekly checks of cannabis inventory will be performed. Any excess cannabis that remains at the end of the data collection period will be destroyed. Cannabis will be ground and mixed with equal parts soil before being discarded.

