Throughout each smoking protocol, a member of the investigatory team will supervise participants to ensure maximal adherence. If the participant engages in behaviors that are likely to augment the cannabis dosage, such as prolonged breath holding, they will be instructed to cease such behaviors. This investigator supervision will ensure that participants are receiving the desired dose of cannabis.

After completion of study procedures, participants will be required to remain in the laboratory for a period of 4 hours beginning from the end of the cannabis inhalation procedure. This period of monitored recovery has been implemented in an effort to minimize the subjective effects of cannabis experienced by participants prior to their release from the laboratory. In addition, participants will be required to complete the drug effects questionnaire each hour following the completion of study procedures. This questionnaire will evaluate the extent to which participants are experiencing the subjective effects of cannabis. If participants indicate that they are still experiencing subjective effects at the end of the 4-hour recovery period via the DEQ, they will be required to remain until effects have subsided. Blood pressure and heart rate will also be monitored throughout the recovery period. Measurements will be taken each hour with the administration of the DEQ.

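### The driving ban ends at midnight on the visit date, so if inhalation ends after 16:00 it gives less than the 8 hours at the top of the protocol's own impairment range

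*Protocol*

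**What the plan says.** Four parts of the protocol bear on driving after a cannabis visit.

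- **Driving rule, section 5.3.** Participants are asked to "Avoid operating a motor vehicle for the entirety of the date of a study visit where cannabis is consumed". The limit is a calendar date, with no number of hours.
- **Escort, section 5.3.** They must also "Arrange to have a trusted individual escort them to their residence following completion of their study visit".
- **Duration of impairment, section 2.3.1.** Directly after the advice not to use cannabis before driving, the protocol states: "Impairment may typically last between 3-4 hours". It then adds a longer and less certain range: "with some evidence indicating that in impairment can persist for 6-8 hours".
- **Supervised stay, section 8.2.** Once the measurements are finished, "participants will be required to remain in the laboratory for a period of 4 hours beginning from the end of the cannabis inhalation procedure". If the drug effects questionnaire (DEQ) still shows subjective effects at that point, "they will be required to remain until effects have subsided". Section 2.3.3 says more generally: "Participants will be monitored until the effects of cannabis have subsided".

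The Schedule of Activities (section 1.3) gives study days only. The text supplied contains no clock window for visits and no latest inhalation time.

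**The concern.** A rule tied to the date protects for a long time after a morning dose and for a short time after an evening one. Impairment runs from the dose and does not follow the calendar. The timed pre-visit restrictions in section 5.3 (cannabis, alcohol, vigorous exercise, caffeine, vitamins, fasting) are all in hours; only the driving rule is tied to the date. After a late enough dose, the written rule would allow driving while the protocol's own upper range for impairment is still running.

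What is at stake is the safety of participants and other road users. No endpoint, estimate or analysis depends on it.

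**Working it through.** The plan gives no figure to reproduce. The check is clock arithmetic on the protocol's own numbers.

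**Inputs**
- Ban ends at 24:00 on the visit date (section 5.3).
- Impairment duration D: typically 3-4 h; some evidence for 6-8 h (section 2.3.1).
- Minimum stay: 4 h from the end of inhalation (section 8.2).
- Clock time T at which inhalation ends: not given, so it is assumed and ranged from 12:00 to 22:00. Impairment is assumed to run from T.

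**Formulas**
- Cover from the date rule = 24 − T.
- Earliest release = T + 4 h.
- Uncovered time outside the laboratory = max(0, D − max(24 − T, 4)). The inner maximum allows for the 4-hour stay.

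| Inhalation ends (T) | Cover from date rule | Earliest release | Uncovered, D = 8 h | Uncovered, D = 6 h |
|---|---|---|---|---|
| 12:00 | 12 h | 16:00 | 0 h | 0 h |
| 16:00 | 8 h | 20:00 | 0 h | 0 h |
| 17:00 | 7 h | 21:00 | 1 h | 0 h |
| 18:00 | 6 h | 22:00 | 2 h | 0 h |
| 19:00 | 5 h | 23:00 | 3 h | 1 h |
| 20:00 | 4 h | 24:00 | 4 h | 2 h |
| 22:00 | 2 h | 02:00 next day | 4 h | 2 h |

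The thresholds are 24 − 8 = 16:00 and 24 − 6 = 18:00. From 20:00 onward the stay replaces the date rule as the binding limit, so the uncovered time stays at 8 − 4 = 4 h or 6 − 4 = 2 h. For D = 3 or 4 h it is 0 h at every T, because max(24 − T, 4) is never below 4.

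**Doses to which the rule applies**
- High-THC doses: section 6.2.1 states that "12 grams of Rex and 4 grams of Kalea will be required". 12 g / 100 mg = 120, which agrees with 20 participants × 6 high-THC visits in section 1.3. With the 3 g of spare Rex: 15 g / 100 mg = 150.
- High-CBD doses: 4 g / 100 mg = 40; with the spare gram, 5 g / 100 mg = 50.
- THC per Rex dose (section 4.3): 100 mg × 13.6% = 13.6 mg; range 100 mg × (13.6 − 2.7)% = 10.9 mg to 100 mg × (13.6 + 2.7)% = 16.3 mg.
- THC per Kalea dose: less than 1% × 100 mg, so less than 1 mg. The point therefore concerns mainly the high-THC doses.

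These counts are all doses in the trial. The number given late is unknown and may be zero.

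**The case against.** The strongest reply is that no gap has been shown to occur. Nothing in the documents puts any inhalation after 16:00. With the 4-hour stay, the 8-hour gap needs release after 20:00 and the 6-hour gap needs release after 22:00. Harm then needs a participant who reports no remaining effects, is escorted home, drives after midnight and is still impaired beyond the typical duration. This stands, and it is why the priority is low.

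The benchmark is also soft. The protocol's main statement is 3-4 hours, and the documents do not say what dose the 6-8 hour figure rests on. By its title, the reference for 3-4 hours studied joints of up to 69 mg THC, about five times the dose here (69 / 13.6 ≈ 5.1), so there is no sign that 3-4 hours is too short for this dose. On the other side, the reference for 6-8 hours is by its title a trial of driving-related performance in young recreational users, which is close to this setting. The 8-hour figure is best read as a cautious upper limit.

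The other safeguards help but do not close the gap. Release beyond 4 hours depends on self-reported subjective effects, while section 2.3.1 also describes impaired cognition and memory, which the DEQ is not described as measuring. The escort covers only the trip home. For participants who withdraw after inhaling, sections 7.1 and 7.2 require the 4-hour stay without repeating the DEQ-based extension, although the general statement in section 2.3.3 may still apply.

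Finally, the consent pages were not available for review and may already give driving advice. That also stands.

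**Conclusion.** The point holds as a conditional and minor one. If inhalation ends after 16:00, the rule in section 5.3 gives less than 8 hours; after 18:00, less than 6 hours. Once the mandatory stay is counted, the uncovered time outside the laboratory is at most 4 hours against the 8-hour figure and 2 hours against the 6-hour figure. Against the typical 3-4 hours there is no gap at any clock time, and for inhalation ending before 16:00 the date rule is already stricter than 8 hours.

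This rests on two assumptions: that some visits run late, which the documents neither show nor exclude, and that the less certain 6-8 hour range is a reasonable safety benchmark because the protocol itself cites it. The change is worth making because it is cheap. It is an optional safety improvement and does not bear on the validity of the trial.

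**What to change.** Keep the date rule in section 5.3 and add one clause to it: *or for at least 8 hours after the end of inhalation, whichever is later*. The uncovered time against the 6-8 hour range is then zero at every clock time.

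The hours limit should not replace the date rule. For inhalation ending at 11:00 the date rule gives 24 − 11 = 13 hours, so an 8-hour limit alone would remove 13 − 8 = 5 hours of cover.

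If the consent form already contains such a limit, only section 5.3 needs to be aligned with it. The cost is one clause and a small inconvenience for participants seen late in the day. Nothing changes for those whose inhalation ends by 16:00.
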